 - i. Boys: <https://www.cdc.gov/growthcharts/data/extended-bmi/BMI-Age-percentiles-BOYS-Z-Scores.pdf>
 - ii. Girls: <https://www.cdc.gov/growthcharts/data/extended-bmi/BMI-Age-percentiles-GIRLS-Z-Scores.pdf>
6. History of prescription for therapeutic gum chewing and/or use of edibles in treatment program
7. Previous tongue tie releases (frenuloplasty and frenectomy)
8. Any therapeutic oral device treatment
9. Previous or current treatment from any other dental, OMT or orthodontic provider
10. Gross neglect of patient's oral health and presence of dental caries
11. Grade 4 tonsils on Brodsky scale

Screening Criteria

1. Accepts Myo Munchee on first presentation
2. Tolerates initial examination including taking measurements
3. Agrees to not seek out other medical treatment for their dental or OMD issues
4. Insufficient nasal patency - proxy for enlarged adenoids - unable to complete the Rosenthal test by reaching 20 breaths through nose with mouth closed ([reference](#))

Materials

1. Myo Munchees
 - a. Mini: 1.5 years - 4 years
 - b. Junior: 4 - 8 years
2. OMT materials
 - a. Dusico Balloon
 - b. Tongue depressor
 - c. Veggie straw
3. Dental materials
 - a. iTero: <https://itero.com/en-AU>
 - b. Palatometer - image 3 - [link](#)
 - c. Caliper - <https://www.harborfreight.com/hand-tools/measuring-marking/calipers-micrometer/calipers.html>

Methods

Power Calculation

With n=12 subjects per group (1 control and 3 treatment groups), totaling 48 subjects overall, we will have at least 80% power to detect a LARGE¹ effect size (defined as mean difference relative to pooled standard deviation) of 1.2 or higher between any of the treatment groups and control group. With 6 subjects in the control group and 12 subjects in the treatment group, we will only have a power of 60% to detect an effect size of 1.2 or greater.

To have 80% power to detect a medium ($d=0.6$) effect size between any of the treatment groups and control, we would require n=45 subjects per group.

Method of treatment group allocation

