- Sleep inventory - <https://www.sleepinventory.com/>
- Children's Airway Screening Taskforce

Patient Recruitment

Patient recruitment process

Refer to Appendix for detailed description

Marketing and advertising materials for recruitment

Informational A4 letters for each individual practice have been developed so patients can read and understand what is required to participate in the study. Refer to Appendix for an example.

Financial Information

Compensation to patients for Participation

The compensation associated with participating in the study will be broken into treatment groups.

1. Myo Munchee only group

- a. Free Myo Munchee device
- b. Follow up measurement appointments at T10 and T26: covered by Myo Munchee
- c. Treatment appointments: all 15-minute appointments covered by Myo Munchee
- d. \$250USD voucher if fulfill these criteria:
 - i. Attend all measurement appointments (3 total)
 - ii. Complete all monthly compliance logbooks (6 total)
 - iii. Attend minimum 6 out of 7 of the 15-minute treatment appointments (7 appointments)

2. OMT only group

- a. \$250USD voucher if fulfill these criteria:
 - i. Attend all measurement appointments (3 total)
 - ii. Complete all monthly compliance logbooks (6 total)
 - iii. Attend minimum 6 out of 7 of the 30-minute treatment appointments (7 appointments)

3. Myo Munchee and OMT group

- a. Free Myo Munchee device
- b. \$250USD voucher if fulfill these criteria:
 - i. Attend all measurement appointments (3 total)
 - ii. Complete all monthly compliance logbooks (6 total)
 - iii. Attend minimum 6 out of 7 of the 30-minute treatment appointments (7 appointments)

4. Control group

- a. Free Myo Munchee device at end of study
- b. \$250USD voucher if fulfill these criteria:
 - i. Attend all measurement appointments (3 total)

The \$250 USD voucher that can be spent at one or split across multiple practices

Costs for Participation

The costs associated with participating in the study will be broken into the treatment groups and to the specific appointments below:

1. Myo Munchee only group

- a. Measurement appointments:
 - i. Initial appointment: billed to patient's insurance provider as an initial evaluation consultation

2. OMT only group

- a. Initial and follow up measurement appointments: billed to patient's insurance provider as an initial evaluation consultation

- b. All treatment appointments: billed to patient's insurance provider as OMT has established therapeutic benefit

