3. Myo Munchee and OMT group
 - a. Initial and follow up measurement appointments: billed to patient's insurance provider as an initial evaluation consultation
 - b. All treatment appointments: billed to patient's insurance provider as OMT and Myo Munchee has established therapeutic benefit
4. Control group
 - a. No cost

Ethics

- To be submitted to Allendale Investigational Review Board - <https://www.allendaleirb.com/>
- Email: [contact]
- <https://www.wma.net/policies-post/wma-declaration-of-helsinki-ethical-principles-for-medical-research-involving-human-subjects>

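### The T10 and T26 visits that yield the primary palatal outcomes cost the family nothing in two arms but are billed to insurance in both OMT arms, an avoidable risk of arm-dependent missing data

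*Protocol*

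**What the plan says.** The payment rules are in the Protocol's Financial Information section, under Compensation to patients for Participation and Costs for Participation.

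- **Myo Munchee only (Group A):** "Follow up measurement appointments at T10 and T26: covered by Myo Munchee" and "Treatment appointments: all 15-minute appointments covered by Myo Munchee". Only the initial measurement visit goes to the insurer.
- **OMT only (Group B):** "Initial and follow up measurement appointments: billed to patient's insurance provider as an initial evaluation consultation". Treatment visits follow the same route: "All treatment appointments: billed to patient's insurance provider as OMT has established therapeutic benefit".
- **Myo Munchee + OMT (Group C):** the measurement-visit wording is the same as for Group B. For treatment visits: "All treatment appointments: billed to patient's insurance provider as OMT and Myo Munchee has established therapeutic benefit".
- **Control (Group D):** listed as having no cost.

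Every arm can earn a $250 voucher, and one condition is common to all four: "Attend all measurement appointments (3 total". In control it is the only condition. The three treatment arms must also complete six monthly logbooks and attend at least 6 of 7 treatment appointments.

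The Measurement and Treatment Timeline places dental measurements at T0, T10 and T26, and its footnote puts allocation after eligibility is confirmed. The three primary outcomes (palatal width, depth and vault height) are all dental measurements. The Power Calculation reads "With n=12 subjects per group (1 control and 3 treatment groups), totaling 48 subjects overall", for an "effect size (defined as mean difference relative to pooled standard deviation) of 1.2 or higher between any of the treatment groups and control group", and makes no allowance for dropout.

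**The concern.** T10 and T26 are research measurements that every arm undergoes, including untreated controls. The protocol gives a reason for billing the treatment visits of the OMT arms (established therapeutic benefit) but none for billing their follow-up measurement visits when those of the other two arms are free. A family's exposure therefore depends on the arm drawn, and it applies after randomisation, when loss can differ between arms. The billing text is also inconsistent on its face, since visits at weeks 10 and 26 are to be billed as an initial evaluation.

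Two things are at stake. The first is power in a design with no spare children. The second is the validity of comparing each OMT arm with control and with Myo Munchee only, should the families who leave differ in outcome from those who stay.

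**Working it through.** **1. Cost exposure by arm, as the protocol states it**

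| Arm | T10/T26 measurement visits | Treatment visits | Voucher conditions |
|---|---|---|---|
| A Myo Munchee only | sponsor pays | sponsor pays | 3 measurement visits, 6 logbooks, 6 of 7 treatment visits |
| B OMT only | billed to insurer | billed to insurer | as A |
| C Myo Munchee + OMT | billed to insurer | billed to insurer | as A |
| D Control | no cost | none | 3 measurement visits only |

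In B and C the voucher depends in part on attending treatment visits that are themselves billed. A family in B or C that misses two treatment visits loses the voucher and may still face a bill for T26.

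**2. The plan's own power figures**

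Method: two-sample t test with noncentral t, two-sided 5%. The protocol does not state sidedness; two-sided is assumed because it reproduces the stated figures. Noncentrality = d × √(n₁n₂/(n₁+n₂)), df = n₁+n₂−2.

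- 12 v 12, d = 1.2: 1.2 × √(144/24) = 2.939, df 22, power 80.2% (stated: at least 80%).
- 6 v 12, d = 1.2: 1.2 × √(72/18) = 2.400, df 16, power 61.6% (stated: 60%).
- d = 0.6 at 80%: n = 44.6, so 45 per group (stated: 45).

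The exact n for 80% at d = 1.2 is 11.94, so 12 leaves no slack.

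**3. Loss from one billed arm, control complete at 12, d = 1.2**

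The number lost is an assumption, shown as a range.

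| Lost from billed arm | Noncentrality | df | Power |
|---|---|---|---|
| 0 | 2.939 | 22 | 80.2% |
| 1 | 2.875 | 21 | 78.3% |
| 2 | 2.803 | 20 | 76.0% |
| 3 | 2.721 | 19 | 73.3% |
| 4 | 2.629 | 18 | 70.1% |

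These are t-test figures matching the protocol's calculation. The planned mixed model would still use T10 data from a child lost only at T26, so they describe children with no usable follow-up.

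**4. Possible shift in a completers' mean**

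Let f be the fraction lost and Δ the difference in mean outcome between retained and lost children, in SD. The full-arm mean is (1−f) × retained + f × lost, so the completers' mean differs from it by f × Δ. With Δ assumed to be 0.5 to 1.0 SD:

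- 2 of 12 lost: 0.167 × 0.5 to 0.167 × 1.0 = 0.08 to 0.17 SD.
- 3 of 12 lost: 0.25 × 0.5 to 0.25 × 1.0 = 0.13 to 0.25 SD.
- 4 of 12 lost: 0.333 × 0.5 to 0.333 × 1.0 = 0.17 to 0.33 SD.

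This is the shift in a simple mean of completers, not the bias of the planned mixed model, which conditions on arm and on the data observed.

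**The case against.** Several counter-arguments have force.

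- **Billing an insurer is not the same as charging the family.** No co-payment, deductible or rule for the uninsured is stated, and the out-of-pocket cost could be zero. This stands: the point is about exposure to cost, not a known charge.
- **The voucher rewards attending exactly these visits in every arm.** This stands in part. It offsets the difference, but its terms are easiest in control and hardest to meet where the qualifying treatment visits are billed.
- **The mixed model includes arm and every child with a baseline, and allows adjustment for demographic variables.** This also stands in part. Loss explained by arm and observed data is handled. Loss related to unobserved outcome is not, for example where families weigh the cost against unrecorded progress, or where insurance status predicts outcome and is not modelled. A child who misses both T10 and T26 contributes no observed change.
- **Funding two time points leaves larger differences in place.** This stands. Treatment-visit billing would still differ, as would the stated total time commitment (about 39, 49, 80 and 6 hours for A to D).

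A reader might also infer that the arrangement favours the sponsor's product. The protocol does not support that: Group C receives the device too and is billed. If children doing poorly left Group B, its completers' mean would be overstated, which would favour OMT over Myo Munchee only.

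**Conclusion.** The point holds as a design weakness that is cheap to remove. Exposure to cost for the visits supplying the primary outcomes depends on randomised arm, no reason is given for this, and one child without follow-up in a billed arm takes its comparison with a full control arm below 80% (78.3%); four take it to 70.1%. Under the assumed 2 to 4 of 12 lost and a 0.5 to 1.0 SD difference between lost and retained children, a completers' mean would shift by about 0.08 to 0.33 SD.

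The protocol does not support the stronger reading that the trial's comparisons are biased. It gives no dropout rate and no out-of-pocket cost, and it shows no link between insurance status and palatal change. The supportable statement is that comparisons of the OMT arms with control and with Myo Munchee only could be biased if loss also relates to unobserved outcome, which the mixed model would not correct. The comparison of the two OMT arms with each other is left aside, because the power statement covers only treatment groups against control.

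**What to change.** State in both Compensation and Costs for Participation that the sponsor covers the T10 and T26 measurement visits in all four arms, as it already does for Myo Munchee only. If that is too much, cover at least the dental visits, which yield the primary outcomes. Remove the initial-evaluation label from the follow-up visits of the two OMT arms.

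The cost falls on the sponsor: 12 + 12 = 24 children × 2 time points = 48 dental appointments, plus 48 SLP appointments if both are covered. All are already scheduled, so no visit, staff or procedure is added. The change removes one arm-specific cause of missing primary data. It reduces arm-dependent attrition but does not remove it, because treatment-visit billing and time burden would still differ between arms.

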Linear mixed model with random subject intercept will be used to compare treatment and control groups. Adjustments for demographic and clinical variables will be performed if necessary. The main statistical analysis will be performed using intention-to-treat (ITT) principle with a secondary per-protocol analysis. For the ITT analysis, all subjects with at least baseline measurements will be included, while for the per-protocol analysis, only subjects who did not deviate from the protocols will be included.

All statistical hypothesis testing will be performed using 5% significance level.

Measurements

Clinical Measurements

Dental Measurements

[Videos](#) demonstrations of measurement taking process.

- **Palatal transverse width** - measured at the primary canines (cusp tips) and the lingual surface of the 2nd molars (narrowest distance measured at gingival margins):
 - a. Anterior intercanine measured between the primary canines (cusp tips) - Image 2a of Thilander et al. 2009.

[figure not shown]

Figure. Image taken from Figure 2a of Thilander et al. 2009

- b. Posterior intermolar measurement between the lingual surface of the 2nd molars (narrowest distance measured at gingival margins): Bogue index

JOUR. A. M. A.
DEC. 2, 1922

the width of the maxillary arch
determines whether or not there is room for normal
nasal breathing.

Figure. Image taken from Bogue, E.A. 'The Relations of the Dental Arches to Pathologic Affections of the Nasopharynx'. Amer Med. Assoc., Transactions of Section on Dis. of Childhood, 58:110 (1907).

- **Palatal sagittal depth/length** - measured anteriorly from the incisive papilla perpendicularly to a line connecting and posteriorly along the same line perpendicular to the disto-gingival margins of the 2nd molars (at alveolar crests);
 - a. Posterior depth/length: Figure 3 from Thilander et al. 2009

[figure not shown]

Figure. Image taken from Figure 3a of Thilander et al. 2009

(b) Arch Depth

[figure not shown]

Figure. Image taken from Figure 3b of Thilander et al. 2009

- **Palatal vault height:** measured from the center of the line connecting the disto-gingival margins of the 2nd molars (at alveolar crests) down to the contact with the mid-palatal suture.

Palatal Height

Figure. Image taken from Figure 4 of Thilander et al. 2009

- Any changes to patients usual oral routines

C-GASP questionnaire

This survey collects clinical information on the signs and symptoms associated with breathing disturbances.

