- Storage of patient data will be for 15 years from the date the patient consents to be part of the study
- The data will be stored in the USA and Australia

Data safety, security and confidentiality

- Data will be de-identified by the treating practitioner and team in the clinic that the patient attends. Name and address will not be entered into the study database but will be entered into the clinics database. Instead, a patient identification number and month and year of birth will be assigned to the patient and entered into the database along with the email address that the parent enters for online questionnaire completion.

Data access

- The de-identified data will be accessible to the principle investigator and the study coordinator throughout the whole study and the biostatistician at the studies completion.
- The identified data will be stored and accessed by the treating clinicians throughout the duration of the study and while the patient is under their professional care.
- A user logbook of start and stop dates of data access will be maintained
- Data will be hosted in the USA and Australia

Data retention and publication

- Data will be retained for up to 15 years and will be used for journal publication, and presentation purposes

Data reviewing, validation and rectification

- Throughout the study, the data will be reviewed every month
- The data will be reviewed for quality purposes to ensure that accurate and correct information has been added to the database
- There will be inbuilt validation checks in the survey and clinical measurements form that the patients parent and treating clinician complete. This will assist in the user entering the correct data
- If there is clinical information missing, input incorrectly, or a mistake made by the treating clinician, this will be addressed and rectified to ensure that the correct information has been added to the database
- If a survey is incomplete or not attempted altogether. Within 1 week of the survey being sent out the parent will receive a reminder, however, after 1 week they will not receive a reminder and the information will be considered incomplete or missing

Data monitoring

- Independent data monitoring may be required if there are challenges confirming the database record discrepancies between the clinical records and the centralized database used for the study

Software - Patient data collection and storage

- Microsoft OneDrive
- Microsoft Excel
- Microsoft Forms

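### In Groups A–C a second missed treatment appointment or one uncompleted logbook forfeits the whole $250 voucher, the only stated payment tied to T26; in Group D it depends on measurement visits alone

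*Protocol*

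**What the plan says.** The Protocol's section on compensation to patients for participation offers one $250 voucher per family, introduced in each arm as a "voucher if fulfill these criteria". It states no partial or per-visit payment.

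- All four arms: "Attend all measurement appointments (3 total". For Group D (control) this is the only condition.
- Groups A, B and C also: "Complete all monthly compliance logbooks (6 total", with no tolerance.
- Group A (Myo Munchee only) also: "Attend minimum 6 out of 7 of the 15-minute treatment appointments (7 appointments".
- Groups B (OMT only) and C (combination) also: "Attend minimum 6 out of 7 of the 30-minute treatment appointments (7 appointments".

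Group D is also promised a "Free Myo Munchee device at end of study". Groups A and C receive a device with no such timing.

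The palatal dimensions are the primary outcomes, and the dental measurements are scheduled at T0, T10 and T26. The Data Analysis section makes ITT the main analysis, using a linear mixed model with a random subject intercept: "For the ITT analysis, all subjects with at least baseline measurements will be included".

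**The concern.** An ITT comparison needs children measured whether or not they keep to treatment. In Groups A–C the voucher rule works against that. Once a family has missed two treatment appointments or one logbook, the $250 is gone, and no other stated payment depends on coming to T26. A control family with the same measurement attendance is paid in full.

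Missing T26 values could therefore concentrate among less adherent treated children, with no matching mechanism in the control arm. If those children do worse than adherent ones, the observed treated group is selected towards better outcomes and the contrast with control moves in favour of treatment. With 12 children per arm, each lost child is 1/12 = 8.3% of an arm.

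This is separate from who pays for the visits. Group A's T10 and T26 measurement visits are covered by the sponsor, yet the same voucher rule applies there.

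**Working it through.** **The Protocol's own figure.** The Power Calculation states at least 80% power for d = 1.2 with 12 per group. A two-sample t-test (noncentral t, two-sided 5%, sidedness assumed) gives 80.2%, so the figure reproduces. There is almost no margin above 80%. If all 12 controls but only 10 treated children are measured, power is 76.0%; with 9 it is 73.3%. These losses are assumed, since the Protocol gives no dropout rate.

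**Voucher logic.** Five of six logbooks fails the logbook condition. Five of seven treatment visits fails the treatment condition. Either forfeits the full $250 even with 3 of 3 measurement visits.

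**Chance of attaining the voucher.** Assume each event is met independently with probability p. T0 is left out because allocation follows the eligibility visit (footnote to the Measurement and Treatment Timeline), so every randomised child has attended it. Two measurement visits remain.

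- Control: p²
- Treated-only conditions: p⁶ × [p⁷ + 7p⁶(1 − p)]
- Treated, all conditions: the product of the two

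| p | Control | 6 of 6 logbooks | At least 6 of 7 visits | Treated-only conditions | Treated, all |
|---|---|---|---|---|---|
| 0.95 | 0.9025 | 0.735 | 0.698 + 0.257 = 0.956 | 0.702 | 0.634 |
| 0.90 | 0.810 | 0.531 | 0.478 + 0.372 = 0.850 | 0.452 | 0.366 |

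The voucher is attained by 90% of controls and 63% of treated families at p = 0.95, and by 81% and 37% at p = 0.90. The treated-only conditions alone are met by 70% and 45%. With 98% per logbook and 95% per visit they are met by 0.886 × 0.956 = 85%.

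**Possible bias.** Assume an effect of 1.2 SD in adherent children, none in two non-adherent children of 12, and both lost at T26.

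- Full follow-up: 10/12 × 1.2 = 1.0 SD.
- Completers only: 1.2 SD, 20% too large.
- Mixed model with those two children seen at T0 and T10: assume a common within-child correlation of 0.9. The weight on a T10 departure is 0.9/(1 + 0.9) = 0.474.
  - If adherent children show 0.6 SD at T10, the arm mean there is 10/12 × 0.6 = 0.5, which is 0.1 below completers. The T26 estimate is 1.2 − 0.474 × 0.1 = 1.153, or 15% too large.
  - If they already show 1.2 SD at T10, the arm mean is 1.0, which is 0.2 below. The estimate is 1.2 − 0.474 × 0.2 = 1.105, or 10.5% too large.

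Observed T10 values thus remove part of the bias but not all of it.

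**The case against.** Several objections are sound and limit the point.

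- **Stopping treatment is not the same as losing the voucher.** A reader might infer that any child who stops treatment forfeits. The treatment is largely home exercise, and the voucher depends on appointments and logbooks. A family that stops exercising but attends, possibly by video, and returns its logbooks keeps the $250. A fully adherent family that misses one logbook loses it. The bias argument therefore needs forfeiting families to be less adherent on the whole.
- **Very early forfeiture.** A reader might infer that the voucher is routinely lost by T4. That requires missing the initial consultation at T2 as well, so treatment was never begun, and it rests on inferred visit dates. The count itself is unsettled. The compensation section says seven appointments, while the hours under Total Time commitment imply four before T10 and four after.
- **Late logbooks.** The data-review section says that "after 1 week they will not receive a reminder and the information will be considered incomplete or missing". This concerns survey data. It does not say that a late logbook voids the voucher.
- **Size of bias.** A reader might infer a 20% to 33% overstatement (1.2 against 1.0 or 0.9 SD with 2 or 3 of 12 lost). That is a completers' calculation with no effect in the lost children. It ignores T10 data, and it attributes every loss to the voucher.
- **ITT.** No text ends follow-up when treatment stops. T10 and T26 are scheduled for all groups, so the Protocol does not contradict its ITT analysis.
- **Reason for the rule.** Treated families are asked for about 39 to 80 hours, controls for 6. Logbooks are also the compliance record. Rewarding participation is defensible.

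What remains is that one indivisible payment carries both the adherence reward and the follow-up incentive, and it does so only in the treated arms. Scheduling the visits for everyone does not change that.

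**Conclusion.** The point holds as a risk built into the compensation rule. The asymmetry is explicit in the text: Groups A–C can lose the whole voucher through adherence items that do not exist in Group D, and what they lose is the only stated payment tied to T26.

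Whether retention will actually differ, and by how much, cannot be known from the Protocol. The attainment figures rest on assumed event rates and on independence. Misses probably cluster within families, which at the same average rate would leave more families meeting every condition. Non-financial reasons to return also remain.

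The direction of bias, in favour of treatment, is conditional on forfeiting families being less adherent and doing worse. In the scenario with 2 of 12 lost, 20% is an upper bound, and T10 values in the mixed model would reduce it. The change is worth making because it is cheap, not because a given bias has been shown.

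**What to change.** Split the same $250. Pay the main part for attending T10 and T26, on identical terms in all four arms, whether or not the child is still attending treatment. Any reward for logbooks or treatment visits should be a smaller, separate part that cannot affect the measurement payment. State in the Protocol and the family information that children who stop treatment are still invited to T10 and T26 and still earn the measurement payments. While editing, reconcile the number of treatment appointments with the hours under Total Time commitment.

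The maximum per family is unchanged. The cost is a wording change, slightly more vouchers paid, and a somewhat weaker incentive for treatment attendance and logbook return. The separate smaller part limits that last effect.

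### OMT only is the one arm never offered the Myo Munchee device and has the least listed compensation, so attrition or outside device use may differ by arm

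*Protocol*

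**What the plan says.** All in the Protocol.

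- **Device (Compensation to patients for Participation).** The lists for Groups A and C each include "Free Myo Munchee device". The control list includes "Free Myo Munchee device at end of study". The list headed "2. OMT only group" has a single item, the 250 USD voucher.
- **Voucher terms (same section).** All arms must meet "Attend all measurement appointments (3 total"). For controls that is the only condition. Group B must also return six monthly logbooks and satisfy "Attend minimum 6 out of 7 of the 30-minute treatment appointments (7 appointments"). Groups A and C have matching terms, with 15-minute visits in A.
- **Visit costs (Compensation, and Costs for Participation).** Group A has "Treatment appointments: all 15-minute appointments covered by Myo Munchee", and the sponsor also pays for its follow-up measurement visits. Group B's measurement and treatment visits go to the family's insurer, the treatment visits being "billed to patient's insurance provider as OMT has established therapeutic benefit". Group C is billed in the same way. Controls have no cost.
- **Exposure before allocation.** Screening Criteria item 1 is "Accepts Myo Munchee on first presentation". The notes to the Measurement and Treatment Timeline place allocation after eligibility is confirmed.
- **Safeguard.** Screening Criteria item 3 asks families not to seek other medical treatment for dental or OMD problems. It does not name the device.
- **Size.** Power Calculation and Treatment Groups both use 12 per arm. No dropout allowance is stated.

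**The concern.** Group B is half of the comparison in the title (Myo Munchee v OMT) and the reference for any add-on effect of the device (C v B). Its families have seen their child accept the sponsor's product, know which arm they are in, carry 90 minutes of home exercises a week, and are in the only arm that never receives the product. The sponsor created this difference, and it falls on the comparator to its own device.

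Two things could follow. Group B children might leave at a different rate from the others, so that missing week 26 palatal measurements depend on arm. Or some Group B families might obtain a device during the trial, which would pull Group B towards Group C and shrink the contrasts that isolate the device. Intention-to-treat analysis does not repair either: it keeps contaminated children in Group B and cannot recover outcomes whose absence depends on arm.

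**Working it through.** **1. Compare the listed packages pairwise.**

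| Arm | Device | Voucher terms | Visit costs |
|---|---|---|---|
| A | During study | 3 measurement visits, 6 logbooks, 6 of 7 treatment visits | Initial visit to insurer; the rest sponsor-paid |
| B | Never | As A | All to insurer |
| C | During study | As A | All to insurer |
| D | At study end | 3 measurement visits only | None |

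C has everything B has, plus the device. A has that plus sponsor-paid visits. D has the same voucher on easier terms, no cost, and a device at the end. On listed compensation, B is last in each of the three comparisons.

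**2. Reproduce the plan's power.** Inputs from Power Calculation: 12 per group and d = 1.2. Data Analysis gives a 5% level; I assume it is two-sided. For a two-sample t-test the noncentrality is d / √(1/n₁ + 1/n₂), with n₁ + n₂ − 2 degrees of freedom.

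- 12 v 12: 1.2 / √(1/12 + 1/12) = 2.94 on 22 df; power 80.2% (stated: at least 80%).
- 6 v 12 gives 61.6% (stated 60%), and 45 v 45 at d = 0.6 gives 80.4% (stated 80%).

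The stated figures reproduce, and 12 per arm sits at the 80% line.

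**3. Illustrate loss from Group B.** The rates are assumed. The other arm keeps 12 and only completers are analysed.

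| Left in B | Power at d = 1.2 |
|---|---|
| 12 | 80.2% |
| 11 | 78.3% |
| 10 | 76.0% |
| 9 | 73.3% |
| 8 | 70.1% |

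For 10 left: 1.2 / √(1/12 + 1/10) = 2.80 on 20 df.

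**4. Illustrate device use in Group B.** If k of 12 Group B children use the device fully, the expected C − B difference shrinks by k/12 of the device effect: 2/12 = 17%, 3/12 = 25%. If the true contrast were d = 1.2 and diluted in that proportion, with 12 v 12 analysed:

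| k | Diluted d = 1.2 × (1 − k/12) | Power |
|---|---|---|
| 1 | 1.1 | 73.1% |
| 2 | 1.0 | 64.9% |
| 3 | 0.9 | 55.9% |

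The same figures apply to A v B only if a Group B child who uses the device is taken to respond like a Group A child.

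**The case against.** The other side has several fair points.

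- **Group B does have a completion reward.** A reader might infer that controls have something waiting at the end and Group B has nothing. That is not so: the Group B voucher depends on all three measurement visits, the last at week 26, and its value is the same in every arm.
- **Group B need not have the weakest reason to stay, or the strongest reason to buy a device.** A reader might infer both. The Protocol supports neither. Group B gets clinician-led therapy that the Protocol describes as of established benefit. Controls are untreated for the whole study and also lack the device during it. Group C has the heavier total time commitment (about 80 hours against 49). Only the ranking on listed compensation is documented.
- **There is a plain rationale.** A device at the end for untreated controls resembles a wait-list offer, and Group B already has an active treatment.
- **Contamination might be noticed.** Changes in oral routine and in activities are recorded, Group B is seen regularly, and a per-protocol analysis is planned. These help detection but do not prevent outside use.
- **The sizes are hypothetical.** No dropout or crossover rate is given. The Protocol powers only treatment against control, so d = 1.2 for A v B or C v B is borrowed. The planned mixed model keeps a child who leaves after week 10, so the completers-only t-test overstates the loss. The dilution figures assume full device use.
- **Families may know all this beforehand.** Consent pages are not shown, so it cannot be said that the difference comes as a surprise after allocation.

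All of these stand as limits on strength. None removes the documented asymmetry, and the Protocol gives no reason for withholding the end-of-study device from Group B alone.

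**Conclusion.** The point holds in a limited form. Group B is the only arm never offered the device and has the least listed compensation. In a trial whose families cannot be masked, and whose children have all accepted the device before allocation, that may make attrition or outside device use differ by arm, at the expense of A v B and C v B. Whether it will do so, and how much, cannot be read from the Protocol. The figures show only that there is no slack: at d = 1.2, two-sided 5%, one child lost from Group B takes a completers-only comparison from 80.2% to 78.3%, and two take it to 76.0%. Bias from who leaves would come on top and cannot be sized here. This is a cheap improvement to the design and not an error in the plan.

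**What to change.** In Compensation to patients for Participation, add to the OMT only list the line that controls already have, "Free Myo Munchee device at end of study", fulfilled after the week 26 measurements. State in the family information, before consent, that every arm receives a device by study end, unless it already says so.

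Cost: at most 12 extra devices and one line in each document. Because the device would be handed over after the last measurement, it cannot affect data already collected.

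The change does not remove the separate difference in visit billing (B and C to insurance, A largely sponsor-paid, D free), which would need its own decision.
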